8.3.6.1.2. Subject Global Satisfaction with Treatment Questionnaire

The subject will be asked to provide a rating of their satisfaction with the treatment results at the at all timepoints after treatment using the Subject Global Satisfaction with Treatment Questionnaire. Following the subject’s completion of the Patient GAIS, the subject will be given the questionnaire to rate their satisfaction with the treatment results. Subjects will be asked how satisfied or dissatisfied they are with how the treated area of the face looks (Appendix 8).

8.4. Safety Assessments

Planned timepoints for all safety assessments are provided in the SOA (Section 1.3).

8.4.1. Physical Examination

A targeted physical examination, [REDACTED], will be conducted at the Screening Visit, Day 1 Visit, and Week 36 Visit or the Final Evaluation Visit, if applicable. Significant physical examination findings that are present prior to investigational product administration are to be included on the Medical History eCRF.

Significant physical examination findings after investigational product administration, which meet the definition of an AE, will be recorded on the AE eCRF post-treatment.

8.4.2. Vital Signs

Vital signs (i.e., body temperature, respiration rate, sitting radial pulse rate, and sitting systolic and diastolic blood pressures) will be obtained at the Screening Visit, Day 1 Visit, and Week 2 and Week 36 or the Final Evaluation Visit, if applicable. Subjects must sit for 5 minutes prior to having pulse and blood pressure measurements taken. Any new abnormal findings or worsening from baseline at subsequent assessments, if judged clinically significant, should be recorded as an AE on the AE eCRF page.

[REDACTED]

[REDACTED]

[REDACTED]

[REDACTED]

8.4.3. Pregnancy Testing

A UPT is required for all WOCBP at screening, baseline (pre-treatment) and Week 36 or Final Evaluation Visit. A positive result prior to treatment will exclude the subject from study participation. The results of the UPT will be evaluated at each study center. If any subject has a positive UPT, a serum pregnancy test is required for confirmation.

If a female subject becomes pregnant while participating in the study, the investigator or site designee must complete the Pregnancy Report Notification Form provided by Revance or designee as soon as the pregnancy is confirmed (see Section 5.6).

8.4.4. Injection Site Evaluation

Injection sites will be evaluated at the Screening Visit to assess for skin inflammation or active skin disease and at the Day 1, Week 2, and Week 4 Visits to determine if there is an immediate reaction to the investigational product. The assessment will be done as a global evaluation of the 3 injection sites for LCL on each side of the face (Table 7). Refer to Appendix 2 for additional information.

Table 7: Injection Site Evaluation

Assessment Descriptor	Present?	
	Yes	No
Erythema		
Edema		
Burning or Stinging (sensation as described by subject)		
Itching (sensation as described by subject)		
Bruising		

If the subject answers yes to any of these items, it should be captured and recorded as an AE in the eCRF.

8.4.5. Clinical Safety Laboratory Assessments

As outlined in Table 8, non-fasting samples for hematology, chemistry, PT (screening only) and urinalysis will be collected at the Screening Visit and the Week 4 and 36 Visits, or Final Evaluation Visit if applicable. [REDACTED]

[REDACTED]. Blood and urine specimens will be collected using applicable safety precautions and will be processed according to the central clinical laboratory's instructions. Urinalysis will be evaluated at the study center using supplies provided by Revance or designee.

[figure not shown]
[REDACTED]

[REDACTED]

[REDACTED]

[REDACTED]	[REDACTED]
[REDACTED]	[REDACTED]

[REDACTED]

8.5. Adverse Events and Serious Adverse Events

8.5.1. Evaluation of Adverse Events and Serious Adverse Events

For this protocol, an **adverse event (AE)** is any untoward medical occurrence (e.g., sign, symptom, disease, syndrome, intercurrent illness, clinically significant abnormal laboratory finding, injury or accident) that emerges or worsens following administration of investigational product and until the end of study participation that may not necessarily have a causal relationship to the administration of the investigational product. An AE can therefore be any unfavorable and/or unintended sign (including a clinically significant abnormal laboratory result), symptom, or disease temporally associated with the use of an investigational product, whether or not considered related to the investigational product. A treatment-emergent AE is one that occurs after any period of exposure to treatment.

Pre-existing conditions, which increase in frequency or severity or a change in nature as a consequence of an investigational product use will also be considered an adverse event.

An unexpected AE is an adverse reaction, the nature or severity of which is not consistent with the applicable product information (e.g., Investigator's Brochure for an unapproved investigational product or package insert/summary of product characteristics for an approved product).

Any change in the study safety evaluations, (e.g., vital signs, injection site evaluation, [REDACTED] [REDACTED]) post-treatment determined to be clinically significant by the investigator must be reported as an AE.

A **serious adverse event (SAE)** is any untoward medical occurrence that results in any of the following outcomes:

- Death
- Life-threatening, (i.e., the subject was, in the opinion of the Investigator, at immediate risk of death from the event as it occurred. It does not apply to an AE that hypothetically might have caused death if it were more severe)
- Persistent or significant disability/incapacity or substantial disruption of the subject's ability to carry out normal life functions
- Requires in-patient hospitalization or prolongs hospitalization (i.e., a prolonged hospitalization beyond the expected length of stay; hospitalizations for elective medical/surgical procedures, scheduled treatments, or routine check-ups are not SAEs by this criterion)
- Congenital anomaly/birth defect (i.e., an adverse outcome in a child or fetus of a subject exposed to the molecule or investigational product before conception or during pregnancy)
- Does not meet any of the above serious criteria but based upon appropriate medical judgement may jeopardize the subject or may require medical or surgical intervention to prevent one of the outcomes listed above (i.e., is a significant or important medical event)

8.5.2. Assessment and Reporting Requirements

The investigator will assess each subject post-treatment and at each subsequent study visit for the occurrence of AEs. In order to avoid bias in eliciting AEs, subjects should be asked the following non-leading question: “How have you felt since your last visit?” All AEs (serious and non-serious) will be collected from the signing of the ICF until the Final Evaluation Visit. Any AE reported by the subject must be recorded on the source documents and eCRFs.

All AEs will be collected from Day 1 until Week 36 or the Final Evaluation Visit at all timepoints as specified in the SOA (Section 1.3). Medical occurrences that begin before the start of study intervention but after obtaining informed consent will be recorded as well.

All SAEs will be recorded and reported to Revance or designee immediately within 24 hours of their awareness of the event. All fatal or life-threatening SAEs should be telephoned to Revance or the designee’s authorized representative as soon as the investigator learns of the event.

[figure not shown]
8.5.3. Serious Adverse Events

The investigator must report an SAE to Revance or the designee’s authorized representative within 24 hours of their awareness of the event:

1. Complete and return an SAE Form with all information known to date; including the investigator’s assessment of causality
2. Contact Revance or the authorized representative for a fatal or life-threatening event as soon as the investigator or study staff are aware of the event
3. Obtain and maintain all pertinent medical records (e.g., discharge summary, autopsy report) and medical judgments of medical personnel who assisted in subject’s treatment and follow-up
4. Provide follow-up information to Revance or designee within 24 hours of awareness

Regulatory Authorities, IRBs/ IECs, and investigators will be notified of SAEs in accordance with applicable regulations and requirements (e.g., ICH-GCP, national regulations and local requirements).

[REDACTED]

[Redacted text block]

[Redacted text block]

[REDACTED]

[REDACTED]

[REDACTED]

[REDACTED]

- [REDACTED]
- [REDACTED]
- [REDACTED]
- [REDACTED]
- [REDACTED]
- [REDACTED]
- [REDACTED]
- [REDACTED]

8.5.5. Follow-up of Non-Serious Adverse Events

All AEs that are identified during the last scheduled study visit (or the Final Evaluation Visit, if applicable) must be recorded on the AE eCRF as ongoing.

Any clinically significant abnormal test results, (e.g., laboratory findings), at the final assessment should be followed to resolution or until determined by the investigator to be stabilized. Repeat tests may be indicated to establish this.

If a subject has any clinically significant, study-related abnormalities at the end of the study, the Medical Monitor should be notified and every effort made by the investigator to arrange follow-up evaluations at appropriate intervals to document the course of the abnormalities unless the Medical Monitor determines that follow-up is sufficient.

8.5.6. Follow-up of Post-Study Serious Adverse Events

Any SAEs that are identified on the last scheduled contact (or at early discontinuation, if applicable) must be recorded on the AE eCRF and reported to Revance or designee according to the reporting procedures outlined in Section 8.5.2. This may include unresolved previously reported SAEs or new SAEs. The investigator should follow these SAEs until the events are resolved, or the subject is lost-to-follow-up. The investigator should continue to report any significant follow-up information to the Medical Monitor, Revance or designee and the IRB/IEC up to the point the event has been resolved. Resolution means the subject has returned to the baseline state of health, or the Investigator does not expect any further improvement or worsening of the subject’s condition.

Any new SAEs reported by the subject to the investigator that occur after the last scheduled contact and are determined by the investigator to be reasonably associated with the administration of investigational product should be reported to Revance or designee and the IRB/IEC.

8.5.7. Investigational Product Causality and Severity

Relationship of an AE to investigational product will be assessed as follows:

- **Definite:** There is a clinically plausible time sequence between the onset of the AE and the administration of investigational product; when the event responds to withdrawal of investigational product and/or recurs with re-administration of investigational product
- **Probable:** There is a clinically plausible time sequence between the onset of the AE and the administration of investigational product; the AE is unlikely to be caused by the concurrent/underlying illness, other drugs or procedures
- **Possible:** There may or may not be a clinically plausible time sequence between the onset of the AE and the administration of investigational product and a cause cannot be ruled out
- **Unrelated:** There is not a temporal or causal relationship to investigational product administration

The investigator is responsible for evaluating all AEs and determining the severity of the event. Severity will be categorized as mild, moderate or severe according to the following definitions:

- **Mild:** Event may be noticeable to subject; does not influence daily activities; usually does not require intervention
- **Moderate:** Event may be of sufficient severity to make subject uncomfortable; performance of daily activities may be influenced; intervention may be needed
- **Severe:** Event may cause severe discomfort; usually interferes with daily activities; subject may not be able to continue in the study; treatment or other intervention usually needed

9. STATISTICAL CONSIDERATIONS

9.1. Statistical Hypotheses

The data from the study running sequentially in cohorts with dose-escalation can be used to assess the maximal tolerable dose level in treating the LCL. It can also be used to assess the effective doses and the potential dose-response. When assessing the dose-response on a responder endpoint, the null hypothesis will be that each dose group has the same rate of response and the alternative hypothesis will be that not all doses groups have the same response rate. That is,

$$H_0: r_1 = r_2 = r_3 = r_4 = r_5 \quad \text{versus}$$

$$H_a: r_i \neq r_j \text{ for at least a pair of dose groups } (i, j), i=1, 2, 3 \text{ or } 4 \text{ and } j=i+1 \text{ to } 5,$$

Where r_i is the response rate for dose group i .

9.2. Sample Size Determination

The sample size is not determined by the power of formal hypothesis tests. [REDACTED]

[REDACTED]

[REDACTED]

[REDACTED]

[REDACTED]

[REDACTED]

[REDACTED]

9.3. Populations for Analyses

For purposes of analysis, the following populations are defined and the summary groups for analysis will be based on the actual dose for LCL received (which is expected to be consistent with the enrollment cohorts):

Population	Description
Enrolled	All subjects who receive the LCL treatment
LCL-Evaluable	All enrolled subjects who have any post-LCL treatment assessment of IGA-LCWS at maximum smile
Safety	All enrolled subjects

9.4. Statistical Analyses

The statistical analysis plan will be developed and finalized before database lock and will describe the detailed methods of analysis, the subject populations to be included in the analyses, and procedures for accounting for missing, unused, and spurious data. This section is a summary of the planned statistical analyses of the primary and secondary endpoints.

In general, descriptive summaries will include means, standard deviations, and range for continuous variables, and counts and proportions for categorical measures. Unless otherwise

stated otherwise, a 95% confidence interval will be provided for means and proportions. No formal hypothesis tests are planned, but group comparisons may be performed as exploratory analyses. No multiplicity adjustments or imputation of missing data are planned.

9.4.1. Efficacy Analyses

Unless otherwise noted, baseline for all efficacy assessments refers to the last available assessment prior to LCL treatment. Efficacy outcomes will be summarized. Descriptive statistics will be provided for all efficacy variables at all timepoints.

The primary efficacy endpoint will be the proportion of subjects achieving a score of 0 or 1 (none or mild) in LCL severity assessed by IGA-LCWS at maximum smile. The LCLs will be evaluated on both sides of the face and both scores will be recorded. If different ratings are obtained from the left and the right sides of the face, subjects will be scored using the higher (i.e., more severe) rating. The dose response in the proportion of responders at Week 4 will be explored using the logistic regression stratified by baseline LCWS severity and study center. Additional measures to assess the effectiveness outcomes will include the investigator GAIS evaluated at maximum smile at each visit. Various responder endpoints associated with the LCWS, such as achieving certain status or certain magnitude of improvement from baseline, will be derived from these effectiveness outcomes for each visit. These responder endpoints will be analyzed by statistical models similar to that for the primary endpoint.

Duration of response will be evaluated by various time-to-event endpoints. Kaplan-Meier (KM) curves will be plotted by dose group for each time-to-event endpoint.

Responder and time-event endpoints defined based on subject assessments for LCL wrinkle severity (such as PLCWS and the subject GAIS for LCL) will be summarized in the same way as those by investigator assessments. Similarly, the endpoints defined based on scores assessed at rest will be summarized in the same way as those on scores assessed at maximum smile.

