
Efficacy Evaluations:
 
• IGA-LCWS• PLCWS• GAIS• FASE• FACE-Q™ Appraisal of Lines: Crow's Feet Lines 
Baseline for all efficacy assessments associated with LCL severity, unless otherwise noted, refers to the last available assessment prior to LCL treatment (Day 1 Visit). Efficacy outcomes derived from the above list of assessments will be summarized descriptively by dose group and by timepoint. Count and proportion will be provided for responder endpoints (defined as proportion of subjects achieving certain status). Kaplan-Meier (KM) curves will be plotted by treatment group for each time-to-event endpoint to assess median duration of effect at maximum smile and at rest for selected endpoints. Dose-response will be explored using logistic regressions on the response rates (of key responder endpoints) and using log-rank test on the time-to-event endpoints. The effect of study center and baseline severity on the treatment outcome will also be explored.

Safety Evaluations:

- Clinical laboratory tests (hematology, serum chemistry, prothrombin time [PT], urinalysis)
 - [REDACTED]
 - [REDACTED]
- Injection site evaluation
 - [REDACTED]
- Concomitant therapies/medications
- Collection of adverse events (AEs)
 - [REDACTED]
- Vital signs
- Physical examination: [REDACTED]

All TEAEs occurring during the study will be recorded and classified according to Medical Dictionary for Drug Regulatory Affairs (MedDRA) terminology. All reported TEAEs will be summarized, in terms of the number of subjects reporting events, system organ class, preferred term, severity, relationship to study drug, and severity. For summarization of event causality and severity, subjects will be counted only once within a system organ class or preferred term for a given event using the event with the greatest relationship for causality and the highest severity. A summary of AEs leading to discontinuation will also be provided.

A by-subject listing of any SAEs will be provided and all SAEs will be summarized by severity and relationship to study treatment.

All AEs, including TEAEs, and SAEs will be summarized for the study overall and by dose group.

Clinical laboratory tests, including serum chemistry, hematology, PT (at the Screening Visit only), and urinalysis will be collected at the Screening Visit, Week 4, and Week 36 or Final Evaluation Visit, if applicable. [REDACTED]

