5.1. Inclusion Criteria

To be eligible for participation, subjects must:

1. Provide written informed consent consistent with International Conference on Harmonisation (ICH)-Good Clinical Practice (GCP) guidelines and local laws, including authorization to release health information, signed prior to any study procedures being performed
2. Be outpatient, male or female subjects, in good general health, 18-65 years old
3. Have a score of moderate (2) or severe (3) LCL at maximum smile effort as assessed by the IGA-LCWS (scores must be consistent bilaterally)
4. Have a score of moderate (2) or severe (3) LCL at maximum smile effort as assessed by the PLCWS (scores must be consistent bilaterally)
5. Have sufficient visual acuity without the use of eyeglasses (contact lens use is acceptable) to accurately assess their facial wrinkles
6. Be willing to refrain from receiving facial fillers, laser treatments, use of any product that affects skin remodeling, or a product that may cause an active dermal response in the treatment areas (e.g., above the oral commissures) from screening through the end of the study
7. All women of childbearing potential (WOCBP) must have a negative urine pregnancy test (UPT) result at the Screening and Baseline Visits and must practice an effective method of contraception throughout the study (e.g., oral contraceptive pill, injection, implant, patch, vaginal ring, intrauterine coil, intrauterine device, tubal ligation, barrier method) used WITH an additional form of contraception (e.g., sponge, spermicide or condom); abstinence; no heterosexual intercourse; or has a vasectomized partner (refer to Section 5.6 for additional information)
8. Able to understand the requirements of the study and be willing and able to follow all study procedures, attend all scheduled visits, and successfully complete the study.

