8.3.1. Investigator Global Assessment of Lateral Canthal Wrinkle Severity

At each clinic visit as designated in the SOA (Section 1.3), the investigator will assess the visual appearance (at rest and at maximum smile) of the LCL on each side of the face using the IGA-LCWS with the following 4-point scale (Table 4).

Table 4: Investigator Global Assessment Lateral Canthal Wrinkle Severity

Rating Score	Lateral Canthal Wrinkle Severity	Description
0	None	None to minimally visible line(s) lateral to the lateral canthus
1	Mild	Visible, shallow line(s) lateral to the lateral canthus
2	Moderate	Clearly visible, moderately deep line(s) lateral to the lateral canthus
3	Severe	Clearly visible, deep line(s) lateral to the lateral canthus with redundancy of skin

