6.5.3.2 Time to Return to, or Time to Loss of, a Given State

The time to return to a given state, or time to loss of a given criterion, will be summarized with point estimates of median duration and 2-sided, 95% CIs, using the log-log transformation by summary cohort. Estimates of survival rates and the 2-sided, 95% CI, using the log-log transformation will also be provided. Kaplan-Meier survival curves will be plotted such that each summary group is a separate line in the same plot. This approach corresponds to the following exploratory endpoints:

- Median time to return to baseline or worse in LCL severity on both the IGA-LCWS and PLCWS at maximum smile

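### No visible rule limits at-rest endpoints to subjects with lines at rest at baseline, so some at-rest outcomes would be settled before treatment

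*Protocol*

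**What the plan says.** **Eligibility.** Inclusion criterion 3 (Protocol 5.1) reads "Have a score of moderate (2) or severe (3) LCL at maximum smile effort as assessed by the IGA-LCWS", and criterion 4 reads "Have a score of moderate (2) or severe (3) LCL at maximum smile effort as assessed by the PLCWS". All eight inclusion criteria are visible, and none sets a score at rest.

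**Scoring.** Protocol 8.3.1 states that "the investigator will assess the visual appearance (at rest and at maximum smile) of the LCL on each side of the face". Protocol 8.3.2 has subjects score themselves in both states. Both scales run from 0 to 3.

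**At-rest analyses.** Protocol 9.4.1 says that "the endpoints defined based on scores assessed at rest will be summarized in the same way as those on scores assessed at maximum smile". The synopsis (Efficacy Evaluations) adds Kaplan-Meier curves "to assess median duration of effect at maximum smile and at rest for selected endpoints".

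**Endpoint forms that are visible.** The primary endpoint is a status endpoint: "proportion of subjects achieving a score of 0 or 1 (none or mild) in LCL severity assessed by IGA-LCWS at maximum smile". Protocol 9.4.1 allows other responder endpoints, "such as achieving certain status or certain magnitude of improvement from baseline". The one return-to-baseline endpoint in the visible SAP (6.5.3.2) is "Median time to return to baseline or worse in LCL severity on both the IGA-LCWS and PLCWS at maximum smile".

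**Populations and denominators.** Protocol 9.3 and SAP 4 define three populations: Enrolled, LCL-Evaluable and Safety. Membership depends on being treated and, for LCL-Evaluable, on a post-treatment investigator score at maximum smile. SAP 6.5 fixes the population count as the denominator of every proportion at every visit.

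**The concern.** At maximum smile, the entry criteria make the endpoints meaningful. Everyone enters at 2 or 3, so a score of 0 or 1 is a real change and everyone has room to improve. At rest there is no such guarantee. Protocol section 2 describes these lines as appearing with muscle contraction first and becoming permanent only over time, so some eligible subjects can be expected to score 0 or 1 at rest before any injection.

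If the maximum-smile forms are used at rest in the whole population, part of each at-rest result is fixed by the baseline score. At-rest response rates could look high without a drug effect, at-rest duration could look short whatever the dose, and differences between cohorts could be diluted or could reflect a different baseline mix. Cohorts are not randomised (SAP 3.1.2) and have about 16 subjects each. The stated effort to balance moderate and severe lines across cohorts (Protocol 4.1) does not mention at-rest scores.

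**Working it through.** The plan gives no at-rest rate, duration or baseline distribution, so it has no figure of its own to reproduce. The only related figure, 4 cohorts × 16 = 64 subjects, is consistent.

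**Step 1: logic by endpoint form, on the 0 to 3 scale**

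| Form carried over to rest | At-rest baseline | Outcome fixed before treatment |
|---|---|---|
| Score of 0 or 1 | 0 or 1 | Already met |
| Improvement of at least 1 grade | 0 | Can never be met |
| Return to baseline or worse, one scale | 0 | Met at the first on-site visit, Week 2 (Protocol 4.4) |
| Return to baseline or worse, both scales | 0 on both | Met at Week 2 |

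**Step 2: size for a status endpoint.** Let q be the share at 0 or 1 at rest at baseline, and r the response among those at 2 or 3. Both are assumptions. If those who start at 0 or 1 stay there, the apparent rate is q + (1 − q)r. With no drug effect r = 0, and the rate is q. The intervals are exact 95% confidence intervals for n = 16.

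| q | Apparent rate, r = 0 | Apparent rate, r = 50% | True contrast of 20% vs 70% appears as |
|---|---|---|---|
| 25% | 4/16 = 25% (7 to 52) | 62.5% | 40% vs 77.5%: 37.5 points |
| 50% | 8/16 = 50% (25 to 75) | 75% | 60% vs 85%: 25 points |
| 75% | 12/16 = 75% (48 to 93) | 87.5% | 80% vs 92.5%: 12.5 points |

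The contrast shrinks by the factor (1 − q), from 50 points when q = 0.

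**Step 3: baseline imbalance.** Take r = 50% in two cohorts, with q = 25% in one and 75% in the other. The apparent rates are 0.25 + 0.75 × 0.5 = 62.5% and 0.75 + 0.25 × 0.5 = 87.5%. That is a difference of 25 points with no difference in effect.

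**Step 4: improvement endpoint.** Let s be the share at 0 at rest. The response rate cannot exceed 1 − s. For assumed s of 25%, 50% or 75%, the ceiling is 75%, 50% or 25%.

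**Step 5: duration.** Now let s be the share at 0 at rest on the scale used, or on both scales for a joint endpoint. With everyone assessed at Week 2, the Kaplan-Meier estimate after that visit is at most 1 − s. If s is at least 50%, the median is the Week 2 visit at every dose. If s is smaller, the early drop remains but does not by itself fix the median.

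**Step 6: effect of restriction.** In subjects at 2 or 3 at rest at baseline, q = 0. The apparent rate then equals r and is 0% with no drug effect. For assumed q of 25%, 50% or 75%, 12, 8 or 4 of 16 subjects per cohort remain.

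**The case against.** A reader might infer that the plan commits itself to an at-rest 0/1 responder rate and an at-rest time to return to baseline, and that the distortions above will therefore occur. The documents do not support that. The sentence in Protocol 9.4.1 concerns how at-rest endpoints are summarised and presupposes that they are defined somewhere. No visible text writes out either definition. Much of the endpoint and derivation text is redacted, including material in SAP sections 5 and 6.5, and a baseline condition may be there. The synopsis limits at-rest duration to selected endpoints, which it does not name.

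A reader might also infer that every subject at 0 at rest on one scale would return to baseline at Week 2. In the joint form of SAP 6.5.3.2 that holds only for subjects at 0 on both scales. Nor is a return at Week 2 peculiar to rest, since a subject who does not improve at maximum smile also meets it. What is peculiar to rest is that a subject at 0 has no other possible outcome.

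Some protection is already planned. SAP 6.2 summarises baseline scores on both scales by cohort, and SAP 6.5.3.3 tabulates change from baseline by category. Protocol 9.4.1 models responder endpoints much as the primary, stratified by baseline severity.

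These points make the concern conditional but do not remove it. The population definitions and the SAP 6.5 denominator rule are visible, and neither refers to at-rest baseline. A redacted definition would have to override that rule. SAP 6.2 and the stratification do not say whether baseline means rest or maximum smile, and stratifying a model does not correct the raw proportions.

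**Conclusion.** The point holds in conditional form. Unless a redacted definition already restricts them, at-rest summaries would include subjects whose result is settled at baseline: automatic responders on a status endpoint, subjects who cannot respond on an improvement endpoint, and automatic Week 2 events on a return-to-baseline endpoint. The direction of the error therefore depends on the endpoint form.

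The size cannot be stated from the documents. Shares of 25% to 75% at 0 or 1 are assumptions, chosen to show that apparent response with no drug effect equals the share itself. The Week 2 median is forced only if at least half the subjects are at 0.

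The consequences are limited. The primary endpoint is at maximum smile and is unaffected. Protocol 9.4 plans no formal hypothesis tests, and the at-rest analyses are descriptive or exploratory. The change is worth making because it is cheap and because at-rest rates or durations read across doses could otherwise mislead.

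**What to change.** State the at-rest definitions in the SAP, align Protocol 9.4.1 with them, and write them as an explicit exception to the SAP 6.5 denominator rule:

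- Summarise at-rest 0/1 response in subjects with an at-rest baseline score of 2 or 3.
- Summarise at-rest improvement of at least 1 grade, and at-rest duration, in subjects with an at-rest baseline score of 1 or more.
- Apply each condition to the scale being summarised. For any joint endpoint, say how the condition applies across the two scales.
- Tabulate at-rest baseline scores by cohort, and make clear in SAP 6.2 that both rest and maximum smile are covered.

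If the redacted text already contains such conditions, the only action is to check that they override SAP 6.5.

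The duration subset should be defined at baseline. Limiting it to subjects who improved after treatment would also remove the automatic events, but it selects on outcome, so the cohorts would no longer be compared like for like. With the baseline subset, a subject who starts at 1 or more and does not improve still has an event at Week 2, as at maximum smile.

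The cost is wording and smaller numbers: for example, 8 of 16 subjects per cohort in the 0/1 table if half are at 0 or 1 at rest, and 4 of 16 if three quarters are. Whole-population tables can be kept alongside, labelled as including subjects without room to improve.
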